### **3. AMENDMENT**

Analysis of the primary outcome after inclusion of 15 patients showed a trend towards a higher end-of-period  $\text{PaCO}_2$  in control mode, but the study lacked statistical power. We thus decided, following the recommendation of our statistician, to make an amendment to the protocol in order to enlarge sample size to 30 patients. This amendment was accepted by our institution's board on July 13th, 2017.

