#### **Authors' contributions:**

MHD designed the protocol, recruited patients, collected data, coordinated the study and will write the manuscript. CR and PAB recruited patients and collected data. MS helped with protocol design. FL supervised the whole process and will review the manuscript.

**Amendments:** sample size enlargement from 15 to 30 patients (July 2017)

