## **2. METHODS**

15 obese patients will be recruited at Quebec's heart and lung Institute. Informed written consent will be obtained from each included patient. The protocol will be submitted to the establishment's ethics committee for approval.

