## **2.3 Sample size**

Since there are few data in the literature regarding the effect of hyperoxia in the obese population, and these data are for patients known to have hypoventilation syndrome and in the stable state, it is difficult for us to estimate the magnitude of the possibly observable change in PaCO2. Based on previous studies on stable OHS patients[16, 17], empirical sample size will be set at 15 patients to detect a PaCO2 difference of 5 mmHg between groups.

[figure not shown]

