## **2.7 Statistics**

Mean differences will be used for all of the outcomes since they are continuous, taking into account the crossover design (analyses with four groups). Univariate and

multivariate analyses will be used to identify factors of response and nonresponse. Analyses to assess period, time and carryover effects will be done.

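### Enrolment was doubled from 15 to 30 because of the primary comparison seen at the full planned sample, and the protocol carries no consequence of that look into the final analysis

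*Protocol*

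**What the plan says.** Section 2 states that "15 obese patients will be recruited at Quebec's heart and lung Institute". Section 2.3 says the "empirical sample size will be set at 15 patients to detect a" PaCO2 difference of 5 mmHg. It gives no standard deviation, significance level or power. No section from 2 to 2.7 plans an interim look.

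Section 3 then reports: "Analysis of the primary outcome after inclusion of 15 patients showed a trend towards a higher end-of-period". The measure is PaCO2, and the same sentence places the higher values "in control mode, but the study lacked statistical power". It continues: "We thus decided, following the recommendation of our statistician, to make an amendment to the protocol in order to enlarge sample size to 30 patients". The front matter lists the same change: "sample size enlargement from 15 to 30 patients (July 2017").

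On the final analysis, Section 2.7 says "Mean differences will be used for all of the outcomes since they are continuous", with allowance for the crossover, and "Analyses to assess period, time and carryover effects will be done". Neither Section 2.7 nor Section 3 mentions the n=15 analysis as something the final analysis must account for. Section 3 gives no estimate, confidence interval or p-value at n=15, and does not say what counted as a trend.

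**The concern.** The first analysis compared the two modes on the primary endpoint, at 100% of the planned sample and 50% of the enlarged one. Its result is the stated reason for continuing. The final sample size therefore depends on the observed treatment comparison.

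Two things follow if the 30 patients are later analysed as though 30 had been fixed from the start:

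- The trial has had two chances to reach significance, if a significant result at n=15 would have been taken as the finding. That is natural when 15 was the planned final size, but it is not stated.
- Half of the pooled data was selected for showing a particular pattern. The pooled estimate and p-value then do not have their usual properties, whatever would have been claimed at n=15.

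This touches the primary endpoint, the only one for which a sample size is given.

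**Working it through.** **Inputs from the protocol.** Crossover with each patient as his own control (Section 2.4); end-of-period PaCO2 as primary endpoint (Section 2.6); looks at n=15 and n=30 (Sections 2.3 and 3); target difference 5 mmHg (Section 2.3).

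**Assumptions, none stated in the protocol.** Two-sided 5% tests; paired t tests on within-patient differences, ignoring the period effect; several readings of 'trend', because Section 3 defines none.

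**The plan's own figure.** The choice of 15 cannot be reproduced, since SD, alpha and power are absent and the size is called empirical. Solved backwards with the noncentral t, 15 patients and 5 mmHg correspond to an SD of the within-patient difference of 6.4 mmHg (80% power) or 5.6 mmHg (90%).

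**Overall type I error.** With p1 and p2 the p-values at n=15 and n=30:

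error = P(p1<0.05) + P(extension occurs and p2<0.05)

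The results below come from 4,000,000 simulated null trials (Monte Carlo SE about 0.0001).

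| Assumed rule for extending | 0.05 at both looks | Part arising at n=30 | Pooled rejection at 0.05, given extension | Look 1 at 0.05, look 2 at 0.0294 |
|---|---|---|---|---|
| Control-higher, p1 0.05-0.10 | 0.0541 | 0.0043 | 0.1718 | 0.0525 |
| Control-higher, p1 0.05-0.20 | 0.0592 | 0.0094 | 0.1253 | 0.0554 |
| Control-higher, any non-significant | 0.0668 | 0.0170 | 0.0358 | 0.0588 |
| Either direction, p1 0.05-0.20 | 0.0686 | 0.0188 | 0.1253 | 0.0609 |
| Any non-significant result | 0.0838 | 0.0341 | 0.0358 | 0.0678 |

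The columns agree with each other. In the second row, 0.0592 - 0.0094 = 0.0498, the first-look rejection rate. Extension there has null probability 0.15/2 = 0.075, and 0.0094/0.075 = 0.125. As a check on the last row, two normal test statistics with correlation sqrt(15/30) = 0.707 give 0.083.

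**If nothing could have been claimed at n=15.** Every false positive then requires p2<0.05, which has probability 5% under the null. Overall error cannot exceed 5%, whatever the extension rule.

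**Bias of the pooled mean.** Patients 16-30 are unaffected by the selection, so

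bias = (expected mean of patients 1-15 given extension - true effect)/2

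After a control-higher p1 of 0.05-0.20, in SDs of the within-patient difference (2,000,000 trials per effect size):

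| True effect | 0 | 0.2 | 0.45 | 0.6 | 0.77 |
|---|---|---|---|---|---|
| Bias | +0.20 | +0.11 | about 0 | -0.06 | -0.13 |

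The selected first half thus averages about 0 + 2 × 0.20 = 0.40 SD when there is no effect, and 0.77 - 2 × 0.13 = 0.51 SD when the effect is 0.77 SD.

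**Patients 16-30 alone.** The false-positive rate given extension is 0.0499 to 0.0506, and the bias is within 0.002 SD, under every rule tried.

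**The case against.** A statistical analysis plan may exist, and the test, alpha and any adjustment could be set there. That stands: a missing alpha is not the point. What remains is in the protocol itself, which made the sample size depend on the observed comparison and drew no consequence from it.

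The protocol is open about the extension and records a statistician's recommendation and board acceptance. A reader might infer concealment, but the text supports the opposite. Disclosure alone, however, does not make a pooled 5% test valid.

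The inflation is modest and conditional. A reader might infer that the error rate is 8.4%. That requires extension after any non-significant result in either direction, the rule furthest from what Section 3 describes. Under the narrow readings the excess is below one percentage point.

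A reader might also infer that a control-higher trend must raise the chance of a false positive at n=30. It does for the p-value bands (12.5% and 17.2%). If 'trend' means any non-significant control-higher result, the figure is 3.6%, below nominal. Nor does the document support saying that the final estimate will overstate the effect: at 0.6 or 0.77 SD the bias runs towards the null.

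Three objections to the remedy also stand in part. A limit assigned after the look does not fully restore control. Patients 16-30 alone are imprecise, so they serve as a sensitivity analysis and not as a replacement. Placing the n=15 result in a protocol still recruiting could influence conduct, since the two modes of Section 2.4 are visibly different, so that result belongs in the final report.

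**Conclusion.** The concern holds in a limited form. The protocol records an unplanned comparative look at the full planned sample, makes it the reason for doubling enrolment, and carries nothing of it into the analysis.

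Pooling all 30 in an ordinary two-sided 5% test is not a valid 5% test if p<0.05 at n=15 would have been claimed. Overall error is then 5.4% to 5.9% on narrow readings of 'trend', 6.7% on the broad control-higher reading, and at most 8.4%. With no possible claim at n=15 there is no overall inflation. Separately, the pooled mean may be biased by about +0.20 to -0.13 SD over true effects of 0 to 0.77 SD, if the first p-value was 0.05-0.20.

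The facts are certain. The size of the consequence rests on the unstated test, claim rule and meaning of 'trend'. A reader might infer that the trial's result is invalid or that an unadjusted pooled test has been chosen; the protocol says neither. This should be fixed, but it is a matter of analysis and reporting and does not defeat the design.

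**What to change.** In Sections 2.7 and 3:

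1. Label the n=15 analysis an unplanned comparative look, state the basis for extending, and commit to reporting its estimate, confidence interval and p-value with the final results.
2. Do not present the pooled n=30 p-value as controlled at an unadjusted 5%. One option is a two-look limit, for example two-sided 0.0294 at n=30, or an equal-weight inverse-normal combination of patients 1-15 and 16-30 with critical value 2.178. The other is to say plainly that the p-value is not controlled at 5%. If a limit is used, state that it was assigned in retrospect. Two-sided 0.0294 holds overall error to about 5% (0.0505 at most in the simulations) only if the first look is held to it too, and leaves about 5.2% to 6.8% if 0.05 would have been claimed at n=15. The choice of limit is the authors'.
3. Report patients 16-30 alone beside the pooled result, as a sensitivity analysis free of the selection.

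**Cost.** No new patients or data. At 0.0294, the difference detectable with 80% power at n=30 rises from 0.529 to 0.575 SD (0.5751/0.5292 = 1.087, or 8.7%). The 5 mmHg target then needs a within-patient SD of at most 5/0.5751 = 8.7 mmHg, compared with 5/0.5292 = 9.4 mmHg at 0.05. Patients 16-30 alone have 48% power at 0.529 SD, and their interval is about 1.5 times as wide as the pooled one (half-widths 0.554 and 0.373 SD; ratio 1.48).
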